9.1.6 Guidelines for Discharge and Follow-up

Discharge: Subjects may be discharged from the hospital at the discretion of the treating attending physician, but the suggested discharge criteria are delineated in Appendix 3.

Medications: Any remaining doses of study medication, as outlined above, will be completed by mouth at home. Subjects will also complete any remaining doses of the 5-day course of azithromycin. Any additional antibiotic therapy can be chosen by the attending physician as deemed necessary for good subject care.

Follow-up: A follow-up appointment in the sickle cell clinic will be made for approximately 1 week after study enrollment and 1 month after discharge. At each visit a standardized interval history (between discharge and the follow-up visit) will be obtained for pain intensity, pain treatment, respiratory symptoms, and any inpatient or outpatient evaluation and management of SCD-related complications.

9.2 Randomization and Masking

After enrollment, subjects will be randomized to one of two treatment arms. Subjects in Arm 1 will receive oral dexamethasone. Subjects in Arm 2 will receive oral placebo. A computer-generated, adaptive randomization schema will be used to allocate subjects 1:1 between the two treatment arms. Randomization will be stratified by site, age and the severity of ACS (see Section 8.3). In order to increase the likelihood of balance in treatment allocations, subjects will be randomized using the standardized range variation (79) of the sequential allocation algorithm of Pocock and Simon (80), a minimization method. This method attempts to achieve treatment balance on several subject characteristics (i.e. age group, site, and severity of ACS in this study) simultaneously – not within separate strata. Minimization consists of biasing the treatment allocation so as to minimize the total imbalance between the treatment groups on some scale (81). The order of entry of the subjects to the various centers and in the various prognostic groups is assumed to be random. As minimization is a dynamic method that uses information on subjects already entered to allocate treatment to the next subject, a continuous updating of the information related to previous treatment allocations is required, thus a centralized randomization system will be used.

Pharmacists at each center will be unblinded and will utilize information from the interactive voice/web randomization system (IVRS) at the SDMC to obtain a new treatment assignment for a subject and provide each subject with appropriate dosing of both therapies. The IVRS system has the capability of providing unblinding information in case of a medical emergency where the exact study drug is needed in order to appropriately treat a subject.

The time interval between Randomization and the first dose of study drug administration will be no longer than 2 hours. In the event a subject's first dose occurs outside the 2-hour time limit, the subject will still be included in the study and the analysis. This is in the spirit of the intention-to-treat analysis. The amount of time in excess of the 2-hour limit until the first dose of study drug will also be recorded. This event will be documented as a protocol deviation.

The subject's physicians, nurses, and ancillary support staff will not be aware of the treatment assignment. The placebo formulations will be identical in appearance and taste to the active compounds (see Section 9.1.3).

9.3 Prior and Concomitant Therapy

No oral or parenteral corticosteroids should have been used in the 14 days preceding enrollment; oral corticosteroids must not have been used in the preceding 3 months; parenteral corticosteroids for respiratory illness must not have been used in the preceding 3 months; and any investigational drug should not have been administered in the preceding 90 days (see exclusion criteria, Section 8.2). There are no other restrictions of prior or concomitant therapy.

9.4 Subject Compliance

Study center personnel or hospital staff nurse caring for the subject will dispense and witness all study drug doses during the hospitalization. Follow-up phone calls to encourage the ingestion of any remaining doses of study drug will be made by the study nurse until the completion of the regimen. The study nurse will also remind and encourage attendance of the follow-up visits during the phone contacts.

10 CLINICAL AND LABORATORY EVALUATIONS

10.1 Efficacy and Safety Assessments

The following efficacy assessments and evaluations will be performed during the study at times outlined in Table 10.2:

- Duration of ACS signs and symptoms (Appendix 3);
- Amount and type of opioid used;
- Number and type (simple or exchange) of transfusions received;
- Duration of hypoxemia;
- Duration of hospitalization;

- Duration of fever;
- Rebound hospitalizations;
- Results of pulmonary function testing (FVC, FEV₁, FEF_{25-75%}, PEFR, and flow-volume loop);
- Pulmonary radiographic findings (resolved, improved, unchanged, and worse); and,
- Rating of pain [Oucher or numeric rating scale (both are 0-10 scales)].

10.2 Safety Assessments

The following safety assessments and evaluations will be performed during the study, at times outlined in Table 10.2:

- Vital signs, including blood pressure;
- Physical examination;
- Urine output and daily fluid balance;
- Blood culture (for fever);
- CBC;
- Reticulocyte count;
- Peripheral oxygen saturation by pulse oximetry;
- AE monitoring;
- Baseline history and interval history (including pain history, pain treatment, respiratory symptoms, inpatient or outpatient evaluations, and management of SCD-related complications); and,
- Concomitant medications monitoring.

10.2.1 Investigational Laboratory Studies (Biomarkers)

All subjects will provide blood for the biomarkers studies on the 4 different days specified in Table 10.1. Approximately 8.5 mL of blood will be needed for the set of assays on a given day; thus a total of approximately 34 mL will be needed for the five sets of assays over the 8-day course of study drug. The baseline sample (Day 0) will be drawn at study entry *before study drug is administered*. Subsequent samples will be timed according to study-drug treatment. The Day 1 sample will be drawn 6-12 hours after the 2nd dose of study drug (this must be before the 3rd dose of study drug is administered). The Day 2 sample will be drawn 6-12 hours after 4 doses of study drug (this must be before the 5th dose is administered), which marks the beginning of the steroid taper. If a subject is discharged from the hospital before receiving 4 doses of high-dose (0.3 mg/kg every 12 hours) dexamethasone therapy, then the Day 2 sample will instead be drawn at the time of discharge, which also marks the beginning of the steroid taper for that individual. In this event, the Day 2 sample should be drawn prior to beginning the steroid taper. The Day 8 sample will be obtained after the completion of the steroid taper. For individuals who received fewer than 4 doses of high-dose (0.3 mg/kg every 12 hours) dexamethasone, the Day 8 sample will be obtained after the completion of the steroid taper instead between Days 7-10. The Day 1, 2, and 8 samples should be drawn 6-12 hours after the preceding dose of study drug and prior to the next dose if applicable. Study personnel will record the date and hour the samples are drawn. If the Biomarker samples cannot be obtained within the indicated intervals, the samples should be collected, nevertheless, as close to the time interval as possible. Study personnel will record the date, time, and reason the samples were collected outside the designated interval.

Samples will be processed and shipped from participating centers to the laboratory of [name] (See Appendix 1) or [name] (See Appendix 4).

Table 10.1 Investigational Laboratory Studies (Biomarkers)

Biomarker Assessed	Baseline (Day 0)	Day 1 (6-12 hrs after 2 nd dose)	Day 2 (6-12 hrs after 4 th dose or discharge)	Day 8 (Day 7-10 or taper end)
Plasma soluble biomarkers (VCAM-1, ICAM-1, P-selectin, L-selectin and vWF multimers).*	X	X	X	X
Flow Cytometry for endothelial microparticles (VCAM ₁ and TF) and monocyte microparticles (TF).*	X	X	X	X
Nitric Oxide metabolites.*	X	X	X	X
Whole blood tissue factor (WBTF).*	X	X	X	X
SPLA ₂ **	X	X	X	X

*[name] Lab

**[name] lab

10.3 Evaluations by Study Visit

10.3.1 Baseline Evaluations

A chest radiograph is necessary for the diagnosis of ACS, the medical care of the subject, and study enrollment. Immediately after enrolling a subject, the elements of the ACS assessment will be assessed and the following additional assessments performed or measurements taken: history (which includes the collection of any transfusions within 24 hours of enrollment), physical exam, vitals signs (includes blood pressure monitoring), a CBC, blood culture (for those subjects with fever), a pregnancy test if applicable, pain intensity (by Oucher or numeric rating scale), and peripheral oxygen saturation (by pulse oximetry) [See Table 10.2.] Additionally, a blood sample will be drawn for the central laboratory measurements (see Table 10.1).

10.3.2 Evaluations During Study

The elements of the ACS assessment will be assessed and recorded every 4 hours (Appendix 3). Note: Time Zero is defined as the initial dose of study drug and the first 24 hour period begins with the first dose. All subsequent doses and study assessments

are scheduled from this time point. The first every 4 hour ACS assessment begins as close as possible to 4 hours after the first dose of study drug and the next routine nursing assessment. The studies required on a daily basis include a CBC and a reticulocyte count. Follow-up blood cultures are obtained at the discretion of the attending physician but should be considered every 24 hours if the subject is persistently febrile (temperature $\geq 38.5^{\circ}\text{C}$). A daily weight, physical exam, and vital signs (every 4 hours which includes blood pressure) will be recorded on the subject's medical record. Subjects will be monitored by continuous pulse oximetry until there has been no requirement for supplemental oxygen for 24 hours and there is clinical improvement. Oxygen saturation (O_2) will be recorded at least every 4 hours with the vital signs until pulse oximetry is stopped. A semi-quantitative, age-appropriate rating of pain intensity [the 0-10 Oucher Scale (age < 10 years) or the 0-10 numeric rating scale (age ≥ 10 years)] will also be obtained by the nurse and recorded with each set of vital signs. A follow-up chest radiograph is not required, but it can be obtained if clinically appropriate. The daily amount and type of opioid analgesia as well as the number and types of transfusions will be recorded. Accurate, cumulative fluid balance measurements (ins and outs) will be recorded every 8 hours on the subject's medical record. AEs will be recorded as they occur throughout hospitalization. The duration of fever, hypoxemia, and hospitalization will also be recorded. Table 10.2 summarizes these evaluations. Furthermore, blood samples will be drawn for the central laboratory measurements at Baseline and Days 1, 2, and 8 (See Table 10.1.).

Table 10.2 Clinical and Clinical Laboratory Evaluations and Procedures

	Inpatient				Inpatient or Outpatient	
	Baseline	Daily	Inter- mittent	Contin- uous	Follow-up #1(7- 10 d) ⁶	Follow-up #2 ⁶
ACS assessment ¹	X		Every 4h		X	X
History	X				Interval ²	Interval ²
Physical exam	X	X				X
Weight	X	X				X
Vital signs	X		Every 4h ⁵		X	X
CBC, reticulocyte count	X	X			X	X
Blood culture	X	X ³				
Chest radiograph	X					X
Pain scale ⁴	X		Every 4h		X	X
Concomitant Medications	X	X	X	X	X	X
Opioids used (quantified)		X				
Pulse oximetry (record every 4 hrs)	X			X (q4h)	spot	spot
Fluid balance (ins and outs)			Every 8h			
Pregnancy test (if applicable)	X					
Study drug administration			Every 12- 24h			
Occurrence of AEs or SAEs				X	X	X
Number of transfusions	X	X			X	X
Pulmonary function testing						X
Compliance					X	X

¹Appendix 3.

²Includes pain history, pain treatment, respiratory symptoms, inpatient or outpatient evaluations and management of SCD-related complications (rebound VOC).

³Only if temperature $\geq 38.5^{\circ}\text{C}$ or at discretion of attending physician

⁴Oucher Scale (age <10 years) or numeric rating scale (age ≥ 10 years)

⁵**Vital signs recorded every 4 h and I/Os every 8 h on subject's medical record. Study personnel will collect the maximum values of the subject's vital signs every 24h.**

⁶**Follow-up #1 is after completion of study drug between days 7-10. Follow-up #2 is thirty days (+/- 3 days) after discharge from hospital and no more than 60 days after study enrollment**

10.3.3 Follow-up Studies

The required measurements and studies at the Follow-up clinic visits are an ACS assessment, CBC, reticulocyte count, oxygen saturation by pulse oximetry, vital signs (includes blood pressure monitoring), and a pain assessment. At each visit, a standardized interval history for pain intensity, pain treatment, and respiratory symptoms will be obtained, as well as any inpatient or outpatient evaluation and management of SCD-related complications which includes the collection of any transfusions the subject received, and an assessment of compliance with the home medications will be completed. AEs occurring after discharge will be captured, especially events requiring hospitalization. **Any additional hospitalizations in the 1 week after discharge for**

VOC will be counted as “rebound VOC” hospitalizations. Additionally, the following will be obtained at the 1-month follow-up only: physical examination, a chest radiograph (PA and lateral views) and pulmonary function testing (PFT) without methacholine challenge or bronchodilators. PFTs will include measurement of forced vital capacity (FVC), forced expiratory volume in 1 second (FEV₁), average forced expiratory flow between 25 and 75% of expired vital capacity (FEF_{25-75%}), and peak expiratory flow rate (PEFR). Also, the flow-volume loop will be recorded and the FEV₁/FVC will be calculated.

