1 SYNOPSIS

[figure not shown]
Title of the Protocol: Randomized Trial of Oral Dexamethasone for Acute Chest Syndrome
Overview: This study tests the effectiveness of oral dexamethasone for the acute chest syndrome (ACS) of sickle cell disease (SCD) in children and adults in the context of standard supportive care. This study primarily aims to determine whether dexamethasone shortens the duration of signs and symptoms of and medical intervention for ACS.
CSCC Protocol Chair: [name].
Intervention: Individuals meeting entry criteria will be randomized to receive either dexamethasone 0.3 mg/kg (12 mg maximum single dose) or an equivalent amount of placebo. The study drug will be given by mouth every 12 hours until discharge from the hospital or for a maximum of 4 doses (2 days), whichever occurs first. Thereafter, study drug will be tapered over 6 days for a total duration of therapy not to exceed 8 days.
IND Holder: [name] #74,481
Objectives: Primary Objective: To determine whether dexamethasone decreases the duration of signs and symptoms of ACS. Secondary Objectives: To determine (1) whether dexamethasone reduces morbidity associated with ACS; (2) whether a tapered regimen of dexamethasone prevents rebound VOC; (3) whether dexamethasone modulates the endothelial phenotype to a less proadhesive, and procoagulant state, and to determine if the discontinuation of dexamethasone will be associated with a rebound in the expression of endothelial activation markers of adhesion and coagulation; (4) whether dexamethasone prevents subacute adverse effects of ACS on pulmonary function; and (5) whether dexamethasone modulates white cell activation and if the discontinuation of dexamethasone will be associated with a rebound in white cell activation.
Hypotheses/Estimates: We will be testing the null hypothesis of no difference in duration of signs and symptoms of ACS among individuals with SCD. The alternative hypothesis tested is that oral dexamethasone is a safe and effective adjuvant treatment that can shorten the duration of signs and symptoms for individuals with SCD who are hospitalized for the treatment of ACS. This is a hypothesis-testing superiority trial.

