6 STUDY OBJECTIVES AND PURPOSE

6.1 Primary Objective:

To determine whether dexamethasone decreases the duration of signs and symptoms of ACS. The duration of ACS will be assessed by ACS Assessment (Appendix 3) that incorporate the resolution of tachypnea, hypoxemia, increased work of breathing, and thoracic pain as well as the cessation of medical interventions to support respiration. We predict that dexamethasone will decrease the time to pulmonary recovery.

6.2 Secondary Objectives:

To determine whether dexamethasone reduces morbidity associated with ACS. We predict that dexamethasone will decrease subjects' pain, the requirement for opioid analgesics, the number of transfusions, the use of supplemental oxygen, the duration of hypoxemia, the duration of hospitalization, and the duration of fever.

To determine whether a tapered regimen of dexamethasone prevents rebound VOC. We will study whether a tapered regimen of oral dexamethasone prevents the recurrence of ACS or the development of other VOC soon after ACS. Abrupt discontinuation of a short course of IV corticosteroid may precipitate an early relapse of VOC. As such, we wish to determine whether a longer, tapered course of oral dexamethasone can prevent the relapse of ACS or VOC and readmission to the hospital. We will also document any treatment-related toxicities.

To determine whether dexamethasone modulates the endothelial phenotype to a less proadhesive and procoagulant state, and to determine whether the discontinuation of dexamethasone will be associated with a rebound in the expression of endothelial activation markers of adhesion and coagulation. We predict that the dexamethasone-treated group will demonstrate a decrease (compared to admission values) in plasma levels of VCAM₁, ICAM₁, P-selectin, whole blood tissue factor (WBTF), tissue factor- (TF-) and VCAM₁-positive endothelial microparticles, and ultra-large vWF multimers (vWF/ULVF) at the 48 hour and discharge blood samplings. Inter-group comparisons (placebo vs dexamethasone) will also demonstrate a decrease following dexamethasone when compared to placebo-treated controls. We also predict that the dexamethasone-treated subject group may demonstrate a rebound in plasma levels of VCAM₁, ICAM₁, P-selectin, vWF, WBTF, and TF and VCAM₁-positive endothelial microparticles concomitant with steroid discontinuation.

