7.1.2 Description of Type of Study

This is a multi-center, randomized, double-blind, placebo-controlled Phase III clinical trial that will include at least 56 subjects with SCD who are hospitalized for ACS. Individuals who meet entry criteria will be randomized to receive either dexamethasone or placebo. Dexamethasone will be administered initially as 0.3 mg/kg by mouth every 12 hours for a maximum of 4 doses (2 days) or until discharge from the hospital, whichever occurs first. Afterward, the study drug will be tapered over 6 days for a total duration of therapy not to exceed 8 days. Due to possible age-related and ACS severity-related differences in the duration of signs and symptoms of ACS, randomization will be stratified by age and severity of ACS (see Section 8.3). We are enrolling a maximum of 112 pediatric subjects. We will enroll adult subjects at the rate site participation will allow, which we anticipate will be no more than 56 subjects. Interim analyses will be performed when a total of 56 subjects and 112 subjects have completed their hospital stay. If we do not stop enrollment after these interim analyses are completed, we will continue to enroll up to a maximum total of 112 pediatric subjects. The efficacy and safety of dexamethasone will be compared to placebo in the context of standard supportive care for ACS.

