9 TREATMENT OF SUBJECTS

9.1 Treatments

9.1.1 Description of Study Drug and Dosing Regimen

Dexamethasone is a commercially available synthetic corticosteroid hormone that is used primarily as an anti-inflammatory agent. It is available in tablets (several manufacturers), and as a solution for IV injection (several manufacturers).

Potential AEs, especially when given chronically, include hypertension, hyperphagia, weight gain, hyperglycemia, striae, acne, osteopenia, personality changes, gastrointestinal ulceration and hemorrhage, and growth retardation. Dexamethasone, like other steroids, may cause avascular necrosis of bone.

The dosing of dexamethasone, or an equivalent amount of placebo, is specified in Table 9.1. The initial dose (0.3 mg/kg every 12H) is given for a total of 2 days (4 doses) or until hospital discharge, whichever occurs first. Note: Time Zero is defined as the initial dose of study drug and the first 24 hour period begins with the first dose. All subsequent doses and study assessments are scheduled from this time point. Afterward, all subjects will receive the taper as specified in Table 9.1. All study drug should be given by mouth. If medications temporarily cannot be given by mouth (e.g. NPO status for a diagnostic test or altered mental status) then the temporary administration of the study drug by vein during this time period is acceptable. The dose of IV study drug is the same as the oral formulation. The study drug should be given by mouth as soon as oral medications can be tolerated.

Table 9.1 Dose and Frequency of Study Drug

Dose (mg/kg)	Max single Dose (mg)	Frequency	24hr dose (mg/kg)	Duration (days)	
0.3	12	Every 12H	0.6	2 (or hospital discharge)	} “High Dose”
0.3	12	Every 24H	0.3	2	
0.2	8	Every 24H	0.2	2	} “Taper”
0.1	4	Every 24H	0.1	2	

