11.6.1 Reporting of Serious Adverse Events

SAE reporting will begin with events that arise after the informed consent is signed until 30 days after the last dose of study drug. Within 1 day of the realization that an SAE has occurred to a study subject, a study investigator must make an initial report CSCC Statistics and Data Management Center SAE Regulatory Specialist. The report should describe the event as fully as possible. The initial SAE reports received from the site should include the following minimum information: an identifiable subject; study product; an identifiable reporting source; and an event or outcome that can be identified as serious. Supporting documentation (e.g., CRF pages, lab reports, summary notes, autopsy reports) should accompany the report.

All participating sites will be expected to report fatal or life threatening SAES to their local IRBs according to standard institute guidelines and procedures.

The site investigator, the Medical Monitor, and the SDMC SAE Regulatory Specialist will collaborate to prepare a report of the SAE using the current version of the FDA’s SAE reporting forms. A fatal or life-threatening unexpected SAE will be reported to the DSMB within 7 calendar days of the receipt of the initial report by the SDMC SAE Regulatory Specialist. A non-fatal, non-life-threatening, unexpected SAE will be reported to the DSMB within 15 calendar days of the receipt of the initial report by the SDMC SAE Regulatory Specialist.

The PI will submit the DSMB report to the Chair of the DSMB Subcommittee appointed to monitor this study and to the NHLBI Project Officer. The PI will submit the SAE report to all study investigators. Each study investigator will submit the SAE report to

the local institutional review board (IRB) and other local authorities in accordance with the institution's regulations.

All SAEs, regardless of expected status, are also recorded in the AE section of the study's CRF.

The site investigator will follow the progress of a subject who experiences an SAE until the SAE is resolved or considered stable. When the SAE has not resolved by the report deadline, the site investigator will make follow-up reports in accordance with directions from the DSMB and/or the site's IRB.

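### The 1-week rebound window is mostly on-drug time in the dexamethasone arm, so the defined rebound endpoint and alert cannot separate prevention from delay

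*Protocol*

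**What the plan says.** Section 6.2 sets the aim: "To determine whether a tapered regimen of dexamethasone prevents rebound VOC". It goes on to ask "whether a longer, tapered course of oral dexamethasone can prevent the relapse of ACS or VOC and readmission to the hospital". The background in section 5 attributes rebound to what happens after steroid withdrawal.

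Section 10.3.3 defines the event: "Any additional hospitalizations in the 1 week after discharge for" VOC are the rebound hospitalizations. The endpoint list (7.1.1), the analysis section (13.2.2), the rebound alert (11.6.6) and Appendix 2 give no other window, so I read all of them as using this one.

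On the drug course, section 9.1.1 says the high dose "is given for a total of 2 days (4 doses) or until hospital discharge, whichever occurs first". Section 7.1.2 adds: "Afterward, the study drug will be tapered over 6 days for a total duration of therapy not to exceed 8 days". After discharge, section 9.1.6 says: "Any remaining doses of study medication, as outlined above, will be completed by mouth at home".

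Later events are collected. A second visit falls about 30 days after discharge with an interval history of inpatient care (Table 10.2, 10.3.3), admissions are followed up by chart review (11.1), and section 11.6.1 says: "SAE reporting will begin with events that arise after the informed consent is signed until 30 days after the last dose of study drug".

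**The concern.** The counting clock starts at discharge, but the risk that the objective is about starts when the steroid stops. In the pilots there was no taper, so those two moments nearly coincided: in the 2004 pilot, six doses over 3 days ended near the mean stay of 60.7 h, and almost all of its 7-day window was drug-free. Here most of the same calendar week is still covered by drug.

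Two things depend on this definition: the answer to secondary objective 2, and the quarterly DSMB alert for what Appendix 2 treats as an important safety issue. If the taper only postpones rebound, both could look reassuring because counting stops too soon.

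**Working it through.** **Plan figures first.** The Table 9.1 durations sum to 2 + 2 + 2 + 2 = 8 days. Section 13.4 assumes a dexamethasone stay with log-mean 3.95 and log-SD 0.3, and placebo 4.25 and 0.6. The means exp(mu + sd²/2) are 54.3 h and 83.9 h, a difference of 29.6 h against the stated 30. A Satterthwaite t-test gives 90.1% power at 54 per group, as stated. These planning values are therefore usable here.

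**Overlap.** Let L be hours from first dose to discharge. High doses fall at 0, 12, 24 and 36 h, and taper doses at 48, 72, ..., 168 h. The course ends at 192 h. If L < 48 h, the taper starts at discharge.
- To course end: on-drug hours after discharge = 144 if L < 48, otherwise max(0, 192 - L).
- To last dose: 120 if L < 48, otherwise max(0, 168 - L).
- Drug-free hours in the window = 168 minus the on-drug hours.

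| Stay L | On drug to course end (days) | Drug-free (days) |
|---|---|---|
| up to 48 h | 6.0 | 1.0 |
| 54 h | 5.7 | 1.3 |
| 84 h | 4.5 | 2.5 |
| 168 h | 1.0 | 6.0 |

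Averaged by simulation over the planning distribution for dexamethasone:
- to course end: 5.6 days on drug, 1.4 off; 86% of subjects have at most 2 drug-free days;
- to last dose: 4.6 days on drug, 2.4 off.

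**Effect on the recorded rate (illustration).** The 2004 pilot had 10/32 = 31.25% vs 2/32 = 6.25%, an excess of 25 points. Assume that only this excess is delayed, and that it spreads evenly over W days after the drug. Recorded rate = 6.25% + 25% × (share of the excess falling inside the window).

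| W | Drug-free time from | Share inside window | Recorded rate |
|---|---|---|---|
| 7 days | course end | 20% | 11% |
| 7 days | last dose | 34% | 15% |
| 3 days | course end | 47% | 18% |
| 3 days | last dose | 78% | 26% |

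**Effect on the alert.** I simulated the 11.6.6 rule (Fisher p < 0.025, dexamethasone higher) at the Appendix 2 looks of 22, 44, 66 and 88 subjects, with placebo at 6.25%. The alert fires in about 3-4% of trials at a recorded 11%, 11% at 15%, 20% at 18%, and 56% at 26%, against about 77% if every event is counted. Continuing the 22-subject steps to 168 subjects raises these, for example to about 12% at 11% and 52% at 18%.

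**Effect on a final comparison.** With 56 per arm, power is 15% at 11% and 47% at 18%, against 93% if all events are counted.

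**The case against.** The strongest reply is that the trial does not lose these events. Interval history at the 30-day visit, chart review, and SAE reporting to 30 days after the last dose all record later admissions, and SAEs are tested by arm every quarter. That stands: a reader might infer that the trial cannot tell prevention from delay, but the documents support this only for the defined endpoint and the alert. The SAE test is a weak substitute, since it works at the highest MedDRA level and at p < 0.01, which pools VOC readmissions with other events.

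The pilots also hint at early rebound: 6/22 (27%) within 72 hours in 1998, and 10/32 (31%) within 7 days in 2004. These are small, separate trials, but they make the 3-day rows more plausible than the 7-day rows. Counted from the last dose, the loss is then modest (26% recorded instead of 31%).

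Three further inferences should be resisted.
- The longer drug-free time computed for placebo is not a bias in favour of dexamethasone. Placebo subjects have no steroid to withdraw from, and both arms have the same 168 h at risk.
- Scaling the whole 31% by the drug-free fraction overstates the loss, because background readmissions are not delayed.
- Saying that 6 of the 7 days are on drug fits short stays only. Section 5 cites a mean stay of about 7 days for all ACS patients, and at that stay only 1 day overlaps.

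Finally, rebound is a secondary endpoint, and section 13.3.3 makes its p-value descriptive.

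**Conclusion.** The point holds for the defined endpoint and for the alert. At the planning stay, the dexamethasone arm has on average only 1.4 days (from course end) to 2.4 days (from last dose) off drug in the counting week. A low rebound rate in that week would not show that the taper prevents rebound, and setting it beside the untapered 27% and 31% favours the taper for that reason alone.

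The size of the distortion is uncertain. It rests on stay being measured from first dose, on the planning distribution (which comes from children), and on an assumed timing of delayed rebound that the protocol does not give. Over the range shown, a true 31% would be recorded as 11% to 26%.

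Because the later admissions are already collected, this is a cheap improvement to a definition and not a defect that undermines the trial.

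**What to change.** In sections 10.3.3 and 11.6.6 and in Appendix 2, define a VOC/ACS readmission count over a window of equal length from discharge in both arms that runs well past the end of study drug. Fourteen days would do: 14 × 24 = 336 h, minus at most 144 h on drug, leaves at least 192 h (8 days) drug-free. A window to the existing 30-day visit is an alternative; since that visit may vary by 3 days either way, a fixed cut-off day should be named. Use this count for objective 2 and for the rebound alert, and report time from last dose. Keep the 1-week count as a supporting analysis for comparison with the pilots.

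The window should not run to a fixed day from first dose. The arm discharged earlier would then have more time at risk.

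The cost is a change of text and a rerun of the Appendix 2 simulation with a background rate suited to the longer window. No visit or data item is added. Some additional background VOC admissions will be counted in both arms. Nothing here implies a change to dosing.
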